12.7.5 Immunologic Assessments

Immunological response evaluations for baseline values will be conducted on the leukapheresis sample used to generate the DCs and on a second leukapheresis sample obtained 4 ± 2 weeks after the third immunization. Blood work for immunologic monitoring (9 yellow and 2 red top tubes) will be drawn before basiliximab (Group III only), vaccine #1, and then as described above after vaccine #3 and/or at progression (whichever comes first). For subjects who complete all 10 study vaccines without progressing, an attempt will be made to obtain blood for immunologic monitoring 2-3 times a year at standard Duke neuro-oncology visits and at progression (whichever comes first). The total amount of blood required for this purpose will be about 90 mLs. The immune monitoring blood drawn at vaccine #1 will be analyzed for baseline CCL3 level. Plasma from the yellow top tubes will be collected at each time point listed where immunologic monitoring is done. Blood work for sub-clinical autoimmunity will be drawn before basiliximab (Group III only), or vaccine #1 (all other groups), and repeated only if clinically indicated. Laboratory evaluations to detect subclinical disease will be obtained as follows: serum thyroglobulin Ab (Lab Code 1802105), rheumatoid factor (Lab Code 5560195), antinuclear Ab (Lab Code 5560214), Thyroid Profile (Lab Code 1850277), and CMP (Lab Code 1004261). A comparison of pre-therapy lymphocyte functions to those at intervals after each immunization will be made. These tests may provide evidence for the development of immune responses following DCs immunization and will play an important role in the design of future DC-based clinical trials. Cellular immune responses to pp65 will be measured in a tiered approach. First, PBMCs will be assessed at pre-treatment (leukapheresis) and during treatment for responses to pp65 using a qualified IFN- γ ELISpot. If positive in the ELISPOT assay, pp65 antigen-specific T cell response will be measured by polyfunctional T cell assays using 8-9 color panels previously optimized in our laboratory which includes detection of CCL3 on T cells. The effect of treatment on cytokines and other soluble factors will be assayed in the serum/plasma. Serum/plasma will be measured to determine levels of CCL3 from the blood drawn at the vaccine #1 visit (in ALL Groups), and repeated at the SPECT/CT imaging visits (2 yellow and 1 red top tubes, in Groups I and II only). T_{Reg} kinetics will be measured by using a constellation of markers specific for T_{Regs} such as foxp3, CD25 and CD4.

In addition, blood and tumor samples will be stored for possible future research in the Duke Brain Tumor Immunotherapy Program (DBTIP) Laboratory where all other samples from this study are stored. The samples being stored are ONLY for this study. Our mouse studies being done in the DBTIP Lab are identifying markers that may influence migration, therefore, as other markers are identified, we would like to investigate whether these same markers are identified in human subjects enrolled on this trial.

Gamma interferon-enzyme-linked immunospot (IFN- γ ELISpot) assay

Using a tiered approach as described above, 90 mLs of peripheral blood will be drawn into (9 yellow and 2 reds) vacutainer tubes containing ACD. PBMC will be separated by density gradient centrifugation using Leukosep tubes. Antigen specific T cell responses to pp65 will be measured *ex vivo* by direct IFN- γ ELISpot assay. PBMCs at 2.5×10^5 per well will be stimulated overnight with a pool of synthetic peptide (15-mers overlapping by 11 amino acids, JPT Peptide Technologies, Germany).

Single-use aliquots of the lyophilized pp65 peptide pool will be resuspended to a final concentration of 1 $\mu\text{g/mL}$. Each assay will include test PBMC cultured with no peptide, pp65 peptide pool, PHA (2.5 $\mu\text{g/mL}$), and positive and negative control PBMC wells for pp65 antigen. PBMCs from different visits for each patient will be batch analyzed on one plate. PBMC added to duplicate wells of ELISpot assay plates coated with mouse IgG1 anti-human IFN- γ mAb will be incubated overnight at 37°C, 5% CO₂, washed with PBS/Tween-20, incubated with biotinylated mouse IgG1 anti-human IFN- γ for 1 hour at room temperature, washed with PBS, incubated with avidin-peroxidase complex for 1 hour at room temperature, washed, incubated with substrate (3-amino-9-ethylcarbazole) for 4 minutes at room temperature and spot development will be stopped by distilled water rinse. Spot enumeration by automated analysis with a Zeiss KS ELISpot system will be performed. Results will be expressed as the mean SFC/10⁶ PBMC after subtraction of counts from cells cultured with no peptide.

Polyfunctional Flow cytometry

Polyfunctional T cell analysis will be done in [name] immunology laboratory on samples positive for secretion of IFN- γ by ELISpot after stimulation with pp65. [name] immunology laboratory conducts all the clinical immune monitoring for the Duke Brain Tumor Center. Polyfunctional T cell panels have been developed in our laboratory and optimized for detection of CCL3 in T cells. This process involves the rapid early detection and analysis of the production of TNF- α CCL3, IFN- γ and IL-2 prior to cellular secretion following antigen-specific stimulation *in vitro*. The functional CD4 and CD8 immune response of the patients will be monitored using an 8 color assay.

Isolated PBMC will be stimulated for 6 hours with the pool of 138 peptides spanning the entire pp65 gene. The cells will be stained for the surface markers CD3 (to identify it as a T cell), CD4 (to define as specific helper cell), CD8 (to define antigen specific cytotoxic T cells), CD27, CD28, CD45RO (to identify maturation and activation state) and the intracellular cytokines IL-2, TNF- α and IFN- γ . This procedure allows for the highly sensitive detection of IFN- γ , TNF- α and IL-2-producing cells which are assumed to be specifically responding to the stimulating antigen. This will also allow us to quantitate the change in antigen specific effector, central memory, and effector memory cells following each vaccination and monitor polyfunctional T cell responses.

Serology/Multiplex Platform

CCL3 and levels of other inflammatory soluble factors may be assayed by multiplex platform. Antibody levels to the immunizing antigen may be measured.

T_{Reg} Kinetics

T_{Regs} will be analyzed by flow cytometry using a constellation of markers specific for T_{Regs} included CD4, CD25 and foxp3.

13 SAFETY MONITORING AND REPORTING

13.1 Adverse Events

An AE is any untoward medical occurrence in a subject receiving any of the study drugs (basiliximab, Td or unpulsed DCs for pre-conditioning, ¹¹¹In-labeled DCs, and pp65 DC vaccines) and which does not necessarily have a causal relationship with this treatment. For this protocol, the definition of AE also includes worsening of any pre-existing medical condition. An AE can therefore be any unfavorable and unintended or worsening sign (including an abnormal laboratory finding), symptom, or disease temporally associated with the use of the DCs, whether or not related to use of the DCs. Abnormal laboratory findings without clinical significance (based on the PI's judgment) should not be recorded as AEs. But laboratory value changes that require therapy or adjustment in prior therapy are considered adverse events.

From the time the subject is randomized through 1 month after the subject's last vaccine, all AEs must be recorded in the subject's medical record and adverse events case report form.

AEs will be assessed according to the CTCAE version 4.0. If CTCAE grading does not exist for an AE, the severity of the AE will be graded as mild (1), moderate (2), severe (3), life-threatening (4), or fatal (5).

Attribution of AEs will be indicated as follows:

- Definite: The AE is clearly related to the study drug
- Probably: The AE is likely related to the study drug
- Possible: The AE may be related to the study drug
- Unlikely: The AE is doubtfully related to the study drug
- Unrelated: The AE is clearly NOT related to the study drug

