All enrolled patients will undergo a leukapheresis after resection for harvest of PBLs for generation of DCs. Patients will then receive approximately 6 weeks of standard of care RT and concurrent TMZ at a standard targeted dose of 75 mg/m²/d (please see Package Insert uploaded in eIRB for standard therapy). Patients should start RT within approximately 6 weeks of surgery. Patients who either experience progressive disease during radiation, are dependent on steroid supplements above physiologic levels at time of first vaccination, are unable to tolerate TMZ, or whose DCs or PBLs fail to meet release criteria will be withdrawn from the study and replaced and will not undergo repeat leukapheresis. For patients whose initial leukapheresis yields less than 3 vaccines, repeat leukapheresis may be obtained a minimum of 2 weeks from the previous leukapheresis (and may be repeated as needed) if pre-pheresis blood work is within the Apheresis Center's parameters and as long as this does not cause a significant delay in treatment for the patient. At the post-RT clinic visit where patient's MRI and blood work is evaluated prior to ordering the first post-RT cycle of TMZ, patients will be randomized to receive DC vaccination with one of three treating regimens: Group I: unpulsed DC pre-conditioning prior to vaccination #4; Group II: Td pre-conditioning prior to vaccination #4; or Group III: basiliximab infusions at vaccination #1 and #2 with Td pre-conditioning prior to vaccination #4. As of March 2017 (AMD 49), randomization of patients to Group III has been terminated. Please see Section 9.1.1 for a detailed outline of the randomization strategy for vaccine site pre-conditioning and Section 9.1.7 for a detailed description of the double blinding process. The study cycle of TMZ comprises a targeted dose of 150-200mg/m²/d for 5 days every 5 (± 1) weeks. All patients will receive up to a total of 10 DC vaccines given bilaterally at the groin site unless progression occurs. DC vaccines will be given i.d. and divided equally to both inguinal regions. DC vaccines #1-3 will be given every two weeks, thus delaying the initiation of TMZ cycle 2 for all patients. All remaining TMZ cycles will continue every 5 (± 1) weeks. Before the first DC vaccination, patients will receive 0.5 mL of Td (tetanus and diphtheria toxoids adsorbed) intramuscularly into the deltoid muscle to ensure adequate immunity to the tetanus antigen. The Td vaccine will be obtained through Duke Investigational Chemotherapy Services (ICS) Pharmacy. All patients will undergo leukapheresis again for immunologic monitoring with specific assessment of baseline antigen-specific cellular and humoral immune responses and further DC generations 4 ± 2 weeks after vaccine #3.

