9.1.4 Safety Considerations

Management of Toxicities

If a Grade 3 NCI CTC or greater toxicity is seen that is not attributable to a concomitant medication, co-morbid event, or disease progression that has been documented radiographically or clinically, the next immunization for that patient will be withheld for up to 2 months or until the NCI CTC toxicity improves to a Grade 2 or until the KPS score returns to within 10 points of baseline. However, planned procedures requiring hospitalization, or long-term clinical decline that is now seen in patients years from WBRT, which are clearly not related to study drug, but

are the natural development common in this patient population, will not be considered an unacceptable toxicity nor will have immunizations withheld.

Adverse Event Reporting and Documentation

An “Adverse Event” will be defined as any adverse change from the subject’s pre-treatment baseline condition (which is assessed at the post-RT/TMZ clinic visit), including any clinical or laboratory test abnormality that occurs during the course of research after the time of randomization. Adverse events will be categorized and graded in accordance with the NCI CTC (Version 4).

A “Serious Adverse Event” will be defined as an undesirable sign, symptom or medical condition which: 1) is fatal or life threatening; 2) requires inpatient hospitalization or a prolongation of existing hospitalization; 3) results in persistent or significant disability/incapacity; 4) constitutes a congenital anomaly or a birth defect and/or; 5) medically significant such that it may jeopardize the subject, and may require medical or surgical intervention to prevent one of the outcomes listed above.

A summary of all adverse events (not just those considered related to study drug) that occur following randomization will be kept which will categorize the event by organ system, relationship to treatment, its grade of severity, and resolution. Periodic review by the PI and monthly review at the PRTBTC Adverse Event meeting of the collective adverse events will occur with the intention of identifying any trends or patterns in toxicity. If any such trends are identified, depending on their severity and frequency, a protocol amendment will be considered.

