12.2 Treatment Period

All enrolled patients will then undergo a leukapheresis for generation of DCs and for baseline immunological monitoring. Within 48 hours of leukapheresis, patients will have blood samples taken for the following tests as required by the Duke Apheresis Center: CBC, CMP, ionized Calcium, and β -HCG (for females of child-bearing potential). Total estimated blood volume required for these evaluations is 12-15 mLs. For patients without sufficient venous access for leukapheresis, a temporary central intravenous catheter may be inserted. To prevent the development of hypocalcemia from the citrate used for leukapheresis, all patients will be instructed to take oral Tums, 2 tablets three times a day and at bedtime the day before and the day of the leukapheresis procedure. Patients who have lower levels of calcium will be treated per Apheresis lab standard protocols under the direction of apheresis attending physician. This first leukapheresis will be approximately a 4-hour leukapheresis, and it is estimated that 10-12 L of blood will be processed during this leukapheresis. One red top tube will be obtained prior to each leukapheresis for immune monitoring (approximately 4 mLs).

Table 4. Schedule of Events

Appointment	Time and Range	Tumor Pathology ¹	Physical and Neurologic Exam KPS, MMSE ²	MRI ³	CMV Screen ⁴	CMP and CBC ⁵	Blood for immunologic monitoring and Sub-clinical Autoimmunity ⁶
Screening and Pre-enrollment	Prior to Consent	X	X	X		X	
Consent	Within 6 weeks of OR				X	X	
Leukapheresis ⁷	After Consent					X	X
RT/TMZ	Per SOC (starts within 6 weeks of OR)					X	
Post-RT TMZ cycle 1	Within 4 (±2) weeks of RT			X		X	
Basiliximab Infusion (Group III only)	Day 14 (± 2 days)		X			X	X
Td Booster IM	Day 20 (± 2 days) so long as before V#1						
Vaccine #1	Day 21 (± 2 days)		X				X
Basiliximab Infusion (Group III only)	Day 28 (± 2 days)		X			X	X
Vaccine #2	Day 35 (± 2 days)		X				
Vaccine #3	Day 49 (± 2 days)		X				
Leukapheresis	4 (± 2) weeks after V#3					X	X

¹ WHO Grade IV Glioma with definitive resection prior to enrollment, with residual radiographic contrast enhancement on most recent CT or MRI of <1 cm in maximal diameter in any axial plane.

² Clinical evaluations with each vaccine will include a general physical examination, complete neurologic examination, and KPS rating. MMSE will be performed at baseline only.

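### Routine AE recording starts at randomisation, so harms of the first, pre-randomisation leukapheresis fall outside the AE record for all enrolled patients

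*Combined protocol and SAP*

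**What the plan says.** **Recording window.** Section 13.1 records AEs "From the time the subject is randomized through 1 month after" the last vaccine. Its definition depends on drug exposure: "An AE is any untoward medical occurrence in a subject receiving any of the study drugs". The list covers basiliximab, the pre-conditioning agents, the labelled DCs and the pp65 vaccine, but not leukapheresis. The attribution scale in the same section asks only about relation to study drug.

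**Definition, baseline and summary.** Section 9.1.4 agrees with 13.1. An AE is a change "that occurs during the course of research after the time of randomization". It is judged against a baseline "which is assessed at the post-RT/TMZ clinic visit". The summary holds events "that occur following randomization will be kept".

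**Timing of the procedure.** Section 9.1 states: "All enrolled patients will undergo a leukapheresis after resection for harvest of PBLs for generation of DCs". RT with TMZ comes next, and randomisation is at the post-RT visit. Section 11 treats leukapheresis as the first study procedure, and Section 9.4 counts patients as on study from consent. Section 9.1 allows a repeat when the first yields fewer than 3 vaccines.

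**Nature of the procedure.** Section 12.2 describes about 4 hours, 10-12 L of blood processed, and oral calcium to prevent citrate hypocalcaemia. Where venous access is poor, "a temporary central intravenous catheter may be inserted".

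**Later procedures.** Section 10.1 plans at least two leukaphereses per patient. Section 9.1 and Table 4 place the second 4 ± 2 weeks after vaccine #3.

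**The concern.** The plan starts routine harm recording after a research procedure has already been done in on-study patients. A line complication or citrate reaction at the first leukapheresis has no place in the AE form. If its effect lasts, the post-RT/TMZ baseline absorbs it as a pre-existing condition. A patient harmed by the procedure and then withdrawn never enters the window.

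What is at stake is the AE summary kept under Sections 9.1.4 and 13.1.1 and the annual toxicity summaries in Section 13.2.1. These would describe the vaccine strategy without the first occurrence of a step that every patient must undergo.

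**Working it through.** **1. Order of events.** Consent, first leukapheresis, RT/TMZ (about 6 weeks), post-RT visit with baseline and randomisation, AE window opens. The first leukapheresis, and any repeat before the post-RT visit, therefore precede the window in every patient.

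**2. Patients never randomised.**
- The plan's randomised total is reproduced: 35 + 35 (Section 15.9) + 9 in Group III (Section 9.1) = 79.
- Upper bound from Section 9.1 (maximum 100 enrolled): 100 − 79 = 21, or 21%.
- From the rates in Section 15.9.2 (4 accrued and 3.5 randomised per month): 1 − 3.5/4 = 12.5%. Then 79/0.875 = 90.3, rounded up to 91 enrolled, and 91 − 79 = 12.
- Range: about 12 to at most 21, if every enrolled patient had the procedure.

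**3. Share of planned procedures outside the window.** Assume one leukapheresis per enrolled patient before randomisation and one per randomised patient after it.
- With 100 enrolled: 100/(100 + 79) = 56% before, 79/179 = 44% after.
- With 91 enrolled: 91/(91 + 79) = 54% before.

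**4. The second leukapheresis.** Vaccine #3 is on Day 49 (Table 4), so the second procedure is on about Day 63 to 91 (49 + 14 to 49 + 42). That is inside the window for patients who continue vaccination. If vaccine #3 was the last vaccine given, the window closes 1 month later, and a procedure at 5 or 6 weeks falls outside it.

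**5. Other routes for patients not randomised.**
- Section 12.6.1 lists inability to tolerate leukapheresis as a withdrawal reason, and Section 12.5 has the reason for leaving the study documented.
- Section 12.1 takes source data for screen failures from the medical record.
- Section 12.6.2 does not follow them for survival, and limits safety follow-up to patients who received basiliximab or vaccine.

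These routes leave a trace, but not graded AE data.

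**6. SAE reporting.** Section 13.2.1 gives no start date, and it sends serious, unanticipated, research-related events to the IRB and FDA. Section 13.2 defines an SAE as an AE with a serious outcome, and Section 9.1.4 limits AEs to after randomisation. Section 9.1.4 also carries an SAE definition of its own with no time limit. The text supports either reading.

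**7. What capture would give.** With no events in n procedures, the 95% upper bound on the harm rate is 1 − 0.05^(1/n): 3.0% for n = 100, 3.2% for n = 91, and 3.7% for n = 79. The gain in precision over the second leukapheresis is modest. The larger gain is in who is observed, because the second procedure is seen only in patients who came through the first and reached vaccine #3.

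**The case against.** The strongest reply is that the start point is deliberate and coherent. Sections 9.1.4 and 13.1 agree, and a post-RT/TMZ baseline keeps RT and TMZ toxicity out of the vaccine profile. That stands. It is the reason to limit the fix to events related to the procedure or its venous access, rather than to collect all SAEs from the first leukapheresis.

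Four stronger readings are tempting, and the documents do not support them:

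- *Leukapheresis harms are missed altogether.* The second and later procedures come after randomisation and normally fall inside the window, where all AEs are summarised whatever their cause (Section 13.1.1). The gap concerns procedures before randomisation. What remains for later ones is that they cannot be attributed to the procedure.
- *Patients never randomised leave no harm data.* Withdrawal reasons and medical-record sources are kept, and serious research-related events may be reportable. The separately filed SOPs, monitoring plan and DSMBplus charter may say more.
- *One enrolled patient in five is affected.* The 21 comes from a maximum and an approximate target. The plan's own rates give about 12, some consented patients may not have reached leukapheresis, and enrolment closed in April 2018 at numbers the documents do not give.
- *The treatment comparison is biased.* The procedure precedes randomisation in all groups, and neither Table 1 nor Section 15 contains a safety objective or analysis.

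It is also fair to say that rewording alone achieves little now that enrolment is closed.

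**Conclusion.** The point holds for the first leukapheresis and any repeat before randomisation. Their harms, including those of a temporary central catheter, are outside the AE record for all enrolled patients. About 12 patients, and at most 21 of 100, have no AE record of any kind. These counts assume that planned numbers were reached and that every enrolled patient had the procedure.

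SAE coverage of this period is ambiguous; it has not been shown to be absent. The efficacy and migration analyses are unaffected. The weakness is confined to the description of harm, but it concerns a mandatory study procedure and can still be largely repaired from records.

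**What to change.** - Amend Sections 9.1.4 and 13.1 so that events related to leukapheresis or its venous access, serious or not, are recorded from the first leukapheresis.
- Add a procedure category to the attribution scale in Section 13.1, so that events at later leukaphereses can be attributed too.
- State the SAE start date in Section 13.2.1, and align the two SAE definitions with it.
- Because enrolment is closed, abstract these events from the apheresis and medical records of all leukapheresed patients, including those never randomised. Section 14.3.2 already makes the medical record the primary source.
- Report them in a separate descriptive table with all leukapheresed patients as denominator, apart from the post-randomisation vaccine AE summary.

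The cost is wording and a limited chart review by existing staff. Retrospective capture may miss minor events, and the table should say so.

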13.1.1 Reporting of AEs

A summary of all adverse events (not just those considered related to the study drugs) will be kept which will categorize the event by organ system, relationship to which treatment, its grade of severity, and resolution. Periodic review by the PI and monthly review at the PRTBTC Adverse Event meeting of the collective adverse events will occur with the intention of identifying any trends or patterns in toxicity. If any such trends are identified, depending on their severity and frequency, a protocol amendment will be considered.

